4.15 Adverse event reporting

All adverse events, whether related to the investigational system or not, will be recorded fully and all serious adverse events will be reported in accordance with regulation 16(10)(a) of the

Medical Devices Regulations 2002 (SI618) and Annex X of the Medical Devices Directive 93/42.

The PI will monitor the dark-adaptometry examination in real time and terminate it if a safety signal is identified and considered to be significant.

Statistical Analysis Plan cover sheet

Wearable Dark-adaptometer in Normal Adult Healthy Volunteers

NCT number NCT02674425

Version 2.0 27/01/2017

WONDER STUDY
Evaluation of a novel wearable light-emitting system for measuring dark-adaptation thresholds in normal adult healthy volunteers

Statistical Analysis Plan

Chief Investigator: [name]
Principal Investigator: [name]
Co-Investigator: [name]
Collaborator: [name]

Clinical Eye Research Centre, St Paul's Eye Unit, Royal Liverpool University Hospital, [name]
University of Liverpool, Department of Eye and Vision Science, Institute of Ageing and Chronic Disease, [name]

Statistical Analysis Plan

Cone- and rod-mediated dark adaptation functions were expressed as log threshold luminance vs. time (minutes). The dynamics of participants' visual recovery after the bleach offset were determined by fitting established models of human dark adaptation to collected threshold data. Two models were used: 1) a bi-exponential model, fitting a single exponential function separately to the cone-mediated phase and the rod-mediated phase of dark adaptation; and 2) an exponential bi-linear model, fitting a single exponential to the cone threshold recovery data and 2 linear components (i.e., S2 and S3) to any rod threshold recovery data.

$$\begin{aligned}
 1) \quad D &= \underbrace{\theta_1 + \theta_2 \cdot \exp\left(\frac{-t}{\theta_3}\right)}_{\text{Cone}} + \underbrace{\eta_4 \cdot \exp\left(\frac{-(t - \theta_5) \cdot h(t, \theta_5)}{\eta_6}\right)}_{\text{Rod}} \\
 2) \quad D &= \underbrace{\theta_1 + \theta_2 \cdot \exp\left(\frac{-t}{\theta_3}\right)}_{\text{Cone}} + \underbrace{\theta_4 \cdot (t - \theta_5) \cdot h(t, \theta_5)}_{\text{S2}} + \underbrace{\theta_6 \cdot (t - \theta_7) \cdot h(t, \theta_7)}_{\text{S3}}
 \end{aligned}$$

$$h(t, \pi) = \begin{cases} 0 & \text{if } t - \pi \leq 0, \\ 1 & \text{if } t - \pi > 0. \end{cases} \quad h(t, \pi) = \frac{1}{(1 + e^{-k(t-\pi)})}$$

where θ_1 is the absolute cone threshold at time t after cessation of the bleach; θ_2 is the cone coefficient; θ_3 is the time constant of cone recovery referred to as cone τ ; η_4 is the final rod threshold or rod absolute sensitivity; θ_4 is the slope of the second rod phase (S2), which represents the rate limited restoration of photopigment; θ_5 is the rod-cone transition time from bleach offset or α point; η_6 is the time constant of rod recovery; θ_6 is the slope of the final component (S3) of rod recovery; θ_7 denotes the time from bleach offset to the transition between the second and final components of rod recovery, referred to as β point; and h is a switch function as described.

Both models, respectively as in Eq. 1 and Eq. 2, have previously been shown to provide a suitable approximation of cone and rod photopigment regenerations after near total photopigment bleaches [1–3]. Matlab (The MathWorks, Natick, USA) was used to fit the dark adaptation models to collected data.

For the cone-mediated dark adaptation function, a single exponential fit was used to estimate the cone time constant (τ) and cone sensitivity parameters. The cone τ is the time constant of the exponential model and is an estimate of cone sensitivity recovery speed. The cone sensitivity is the plateau of the exponential function and is an estimate of the absolute threshold of cone photoreceptors.

For the rod-mediated dark adaptation function, the parameters of interest were the rod-cone break (RCB), rod slope, and rod sensitivity. The RCB is the time in minutes after bleach offset at which the rods are more sensitive to the test target than the cones. The rod slope is the slope of the sensitivity recovery during the second (S2) and third (S3) components of rod-mediated dark adaptation described by Lamb et al. [4,5]. The rod sensitivity parameter was measured as the minimum sensitivity value of the rod-mediated dark adaptation function around the 40 minutes end of the test.

Cone- and rod-mediated parameters were compared to previous literature on human dark adaptation to evaluate the performance of the developed dark adaptometer. Clinical data reported in [6] were particularly taken into consideration since a similar DA protocol was used by Jackson et al. to assess dark adaptation changes with age and as a function of decade. In addition, trial outcomes of interest were the test-retest and usability score results and variability obtained from participants after one or multiple DA visits.

Repeatability coefficient (RC) and within-case coefficient of variance (wCV) were calculated starting from the within-subject variance for each trial participant who completed at least 2 DA visits in order to assess variation in repeat measurements on the same patient. Intra-class correlation coefficient (ICC) – 2-way mixed-effects, absolute agreement, average measurement – was calculated for both

Group 1 and Group 2 through SPSS® Statistics V22.0 (IBM, Armonk, USA) to obtain the proportion of total variation in measurements by between-patient differences.

A pen-and-paper questionnaire as in Appendix 1-a was presented to participants twice on completion of the first and the third DA appointment. Seventeen questions targeting hardware and software implementation as well as personal feedback on the duration of the DA test were asked to rate comfort and ease of use of the developed system.

- [1] Alpern M. et al. Rhodopsin kinetics in the human eye. *Journal of Physiology*, 217 (1971), pp. 447-471.
- [2] W.A.H. Rushton, D.S. Powell. The rhodopsin content and the visual threshold of human rods. *Vision Research*, 12 (1972), pp. 1073–1081.
- [4] T.D. Lamb. Spontaneous quantal events induced in toad rods by pigment bleaching. *Nature*, 287 (5780) (1980), pp. 349-351.
- [5] T.D. Lamb. The involvement of rod photoreceptors in dark adaptation. *Vision Research*, 21 (12) (1981), pp. 1773-1782.

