Both cone and rod dark-adaptation curves consist of an initial rapid nonlinear increase in sensitivity (i.e., the S1 component of recovery) followed by a second longer section (i.e., the S2 component of recovery) of near linear slope and a third section (i.e., the S3 component of recovery) where the curve asymptotically reaches the final cone and rod threshold, respectively [18]. The first section of the cone phase curve may be explained by the rapid increase in pupillary diameter [8, 20]. The near linear middle sections are determined by the regeneration of bleached visual pigments in the outer segment discs of the cone and rods [21]. The difference in the decay curve of both cone and rod mediated vision may be explained by different regeneration half-lives of the rod ($t_{1/2} = 5$ minutes) and cone ($t_{1/2} = 90$ seconds) cells thus cone pigments are regenerated at a faster rate than rhodopsin.

Despite the use of more objective modern instrumentation [22-23], the subjective determination of human dark adaptation has provided important information on the structure and functioning of the retina and continues to be a useful investigative tool.

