The absolute threshold will be the last measured threshold and recorded as the dimmest light that the subject can detect when the rod sensitivity of the study eye is maximum. In a healthy adult, the absolute threshold is typically equal to a logarithmic light intensity around 10^{-6} cd/m^2 at a time of around 30 minutes from the start of the test.

The examiner will monitor in real-time the testing results on a laptop, which is USB-connected to the frame of the goggles from the same side of the study eye. A best fit of collected threshold measurements will be calculated; from this fit, a biphasic curve is expected to be observed.

The rod-cone break will be identified as the point of phase-change in the calculated curve, which coincides with the point when rods become more sensitive than cones. In a healthy adult, the rod-cone break is typically equal to a logarithmic light intensity around 10^{-3} cd/m^2 at a time of around 7 minutes from the start of the test.

The slope of the rod-mediated response will be also calculated from the best fit of the collected threshold measurements. Particularly, the slope of the (second) S2 and (third) S3 rod-mediated component of recovery will be identified: these coincide with a long section of near linear slope following the initial rapid nonlinear increase in rod sensitivity.

An ad hoc pen-and-paper system usability questionnaire will be presented to participants twice upon completion of the first and the last dark-adaptometry testing visit. Participants will rate comfort and ease of use of the system on a scale of 1-10 through questions targeting hardware and software implementation as well as testing duration and expectations.

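### The SAP labels θ6 as the S3 slope, but in Eq. 2 θ6 is the change in slope at the β point; the S3 slope is θ4 + θ6, and the SAP does not say which is reported

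*SAP*

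**What the plan says.** The SAP sets the scale first: "Cone- and rod-mediated dark adaptation functions were expressed as log threshold luminance vs. time (minutes". A falling curve, and so a negative slope, means recovery.

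Eq. 2 is the sum of a cone exponential, an S2 term θ4·(t − θ5)·h(t, θ5) and an S3 term θ6·(t − θ7)·h(t, θ7). Two forms of the switch h are printed, a 0/1 step and a logistic function with an unspecified constant k. Both tend to 1 once t has passed the switch time, and neither goes back to 0.

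The list of symbols that follows gives θ4 as the S2 slope and θ7 as the S2-to-S3 transition (the β point), and says "θ_6 is the slope of the final component (S3) of rod recovery". Later in the same section the SAP describes the parameter of interest in words: "The rod slope is the slope of the sensitivity recovery during the second (S2) and third (S3) components". Protocol section 4.8 adds: "The slope of the rod-mediated response will be also calculated from the best fit of the collected threshold measurements". Protocol section 4.12 lists the S2 slope and the S3 slope as two separate secondary outcomes. Neither document writes the S3 slope as a formula in θ4 and θ6.

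**The concern.** The symbol list and the equation give θ6 different meanings. An analyst who follows the symbol list would take the fitted θ6 from the Matlab output and report it as the S3 slope. In Eq. 2 that number is the difference between the S3 and S2 slopes.

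The SAP compares rod-mediated parameters with published values to judge the device, so a mislabelled slope would be set against figures for a different quantity. There may also be an effect on repeatability. The SAP says "Repeatability coefficient (RC) and within-case coefficient of variance (wCV) were calculated starting from the within-subject variance" and adds an intra-class correlation, but does not say for which parameters. If the S3 slope is one of them, θ6 and θ4 + θ6 will in general have different means and variances, and so give different repeatability results.

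**Working it through.** The documents state no figure on this point to reproduce, so the check is algebra followed by illustration.

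**Slope implied by Eq. 2 (step switch).**

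- For θ5 < t < θ7: dD/dt = −(θ2/θ3)·exp(−t/θ3) + θ4.
- For t > θ7: dD/dt = −(θ2/θ3)·exp(−t/θ3) + θ4 + θ6.

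With the cone exponential decayed, S2 = θ4 and S3 = θ4 + θ6. Hence θ6 = S3 − S2.

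**Sign.** Protocol section 2 describes "a third section (i.e., the S3 component of recovery) where the curve asymptotically reaches the final cone and rod threshold", so the curve levels off and S3 is shallower than S2. With both slopes negative and S3 nearer zero, θ6 = S3 − S2 is positive while the S3 slope is negative.

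**Size.** For r = S3/S2 between 0 and 1, |θ6|/|S3| = |S2/S3 − 1| = (1 − r)/r.

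| r | (1 − r)/r |
|---|---|
| 0.1 | 9 |
| 0.2 | 4 |
| 0.5 | 1 |
| 0.8 | 0.25 |

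**Illustration tied to the protocol's typical values.** Section 4.8 puts the rod-cone break near −3 log cd/m² at 7 min and the absolute threshold near −6 log cd/m² at 30 min. Joining these with two straight segments that meet at β requires

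−3 + S2·(β − 7) + S3·(30 − β) = −6, so S2 = (−3 − S3·(30 − β))/(β − 7).

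S3 and β below are assumed; slopes are in log units per minute.

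| S3 | β (min) | S2 | θ6 = S3 − S2 | \|θ6\|/\|S3\| |
|---|---|---|---|---|
| −0.05 | 16.25 | (−3 + 0.6875)/9.25 = −0.250 | +0.200 | 4.0 |
| −0.12 | 20 | (−3 + 1.2)/13 = −0.138 | +0.018 | 0.15 |
| −0.02 | 12 | (−3 + 0.36)/5 = −0.528 | +0.508 | 25.4 |

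**Could the label be literally true?** Take the first row and set θ6 equal to the S3 slope, −0.05. Eq. 2 then gives, at 30 min, −3 − 0.25·23 − 0.05·13.75 = −9.44 log cd/m², against about −6 in the protocol, and the curve steepens after β. With θ6 = +0.20 it gives −3 − 5.75 + 2.75 = −6.00.

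**Fit to simulated data.** One curve with true S2 = −0.25, S3 = −0.05, β = 16 min and noise SD 0.1 (all assumed) was fitted with Eq. 2, using the logistic switch with k = 10. The estimates were θ4 = −0.247, θ6 = +0.195 and θ4 + θ6 = −0.052.

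**Logistic switch.** Mean slope of the two rod terms for the first row (θ4 + θ6 = −0.050):

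| Switch | 25–35 min | 30–40 min |
|---|---|---|
| Step | −0.050 | −0.050 |
| k = 0.3 | −0.041 | −0.047 |
| k = 0.5 | −0.048 | −0.050 |
| k = 1, 2, 5 or 20 | −0.050 | −0.050 |

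The result carries over to the logistic form well past θ7. With a very gradual switch the sum is only approximate inside the test window.

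**The case against.** The best reply is that the SAP does define the reported quantity, in words. Its later paragraph describes rod slope as the slope during each component, and the protocol takes it from the best fit. Read with Eq. 2, that is θ4 + θ6 for S3. The SAP also shows that a symbol's label need not be the reported outcome: η4 is labelled as the final rod threshold, yet rod sensitivity is measured separately as the minimum value near the end of the test. On this reading the fault is a loose label. This has force, and the analysts may well use the sum. But the label is explicit, it conflicts with the verbal description, and nothing in either document says which one governs.

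Other points stand as limits:

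- The harm is conditional on θ6 being the reported figure, and a positive slope on a falling curve might be noticed.
- The illustrations rest on assumed slopes and span 0.15 to 25, so they show that θ6 differs from S3 but not by how much in this study. Protocol section 4.8 describes S2 and S3 together as nearly linear, so r close to 1 cannot be excluded.
- Because k is not given, θ4 and θ4 + θ6 may both be approximations if the logistic switch is gradual. With k = 0.5 and the first set of slopes above, the mean rod slope over 10–14 min is −0.286 against θ4 = −0.25.
- The SAP plans no standard errors for individual fitted parameters, so a covariance-based standard error is needed only if one is reported.

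Reporting slopes as positive recovery rates does not remove the problem. Reversing every sign turns θ6 = +0.20 into −0.20 against an S3 rate of +0.05. Taking absolute values hides the sign, but the size is right only when S3 is exactly half of S2.

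**Conclusion.** The definition of θ6 is wrong as written. The algebra is exact for the step switch once the cone term has decayed, and does not depend on any assumed slope. For the logistic switch it holds well past θ7 unless k is small.

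The consequence is confined to one secondary outcome and to any literature comparison or repeatability statistic based on it. The rod-cone break and absolute threshold do not depend on how θ6 is labelled. The error in the S3 slope, if θ6 is what gets reported, depends entirely on S3/S2, which the documents do not give. It merits correction because a named outcome may be misreported, but it puts no primary result at risk.

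**What to change.** Either of two equivalent changes resolves it:

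1. Keep Eq. 2, define θ6 as the change in slope at the β point, and state that the S3 slope is reported as θ4 + θ6. If a standard error is given, compute it as √[Var(θ4) + Var(θ6) + 2·Cov(θ4, θ6)].
2. Rewrite the last term of Eq. 2 as (θ6 − θ4)·(t − θ7)·h(t, θ7), so that θ6 is the S3 slope as labelled.

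In either case, base any repeatability coefficient, wCV or ICC for the S3 slope on that slope computed visit by visit. State which switch form and which k were used, and confirm which quantity has been or will be reported.

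The cost is one line in the SAP and one line of code. The fitted curve does not change, and the first option needs no refit.

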The typical range from highest threshold luminance to absolute rod threshold covers about 5 logarithm units of luminance [16]. The first part of the curve is the photopic phase, which identifies the cone adaptation. The last part of the curve is the scotopic phase, which identifies the rod adaptation [11]. The interval between the two phases is commonly referred to as the rod-cone break. It can be seen in Figure 1 that, as the luminance is reduced, there is an increase in light sensitivity, which is initially very rapid before levelling off after 5 to 10 minutes at the final or absolute cone threshold [5]. At this point, the foveal cone cells are fully dark adapted (i.e., they have reached their maximum sensitivity [17]); in contrast, the rod cells are saturated and inactive [1]. With time (the luminance of the stimulus is reduced) a second slower fall in the threshold luminance is observed as the peripheral rod cells become activated (rhodopsin is regenerated). Rod adaptation is slower than the cone adaptation [18] because of the regeneration half-life of the visual pigments. However, unlike cone cells, light of very low intensity is capable of stimulating the rod cells, when given sufficient time to accumulate rhodopsin [2]. After approximately 30-40 minutes in total darkness, the final rod threshold is achieved. Dark adaptation is now complete and no further increase in sensitivity of the rods photoreceptors is possible.

The time required to reach maximum sensitivity is dependent on the amount of pigment bleached by the previous light exposure [19] and neural adaptation. The wavelength of the incident light has also a strong influence on the dark-adaptation curve, given that cone mediated vision is responsible for colour vision whereas rod vision is colourless.

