4.3. Investigational system

[figure not shown]

Figure 3. 3-D model of the head-mounted goggles with parts

The novel dark-adaptometer is designed as a wearable and semi-automated system consisting of a pair of head-mounted goggles (Figure 3) and a handheld joystick. Within each side of the goggles are included: an organic light emitting diode (OLED) display, which delivers the light stimuli; and a LCD filter sitting in front of the display to precisely tune the light stimuli within a range between 10^{-6} to 10 cd/m^2 . A handheld joystick completes the system allowing the subject under test to wireless transmit its response to the visible light stimuli through the press of a button. The response is cached and interpreted by the computing unit inside the goggles, which automatically set light intensity and time interval of the successive stimuli based on a modified 3-down-1-up staircase procedure described as in [43] and schematically depicted in Figure 4.

[figure not shown]

Figure 4. Flow-chart of the implemented dark-adaptometry testing procedure

Wearable goggles and joystick are given to participants in their switched-on status and held by the subject under test respectively on the forehead, with an elastic strap, and on the dominant hand. In order to reset the photoreceptors of the retina, thus guarantee a similar non-dark-adapted background common to all participants, a photo-bleaching flash is presented through an external camera and channelled to the study eye at the start of the test. Immediately after the onset of the photo-bleaching flash, the goggles are pulled down over the eyes by the user that will now be exposed to white light stimuli of 200 milliseconds duration. Light stimuli are automatically emitted for the threshold measurements and will stop when the absolute threshold is measured, which in normal healthy adults typically occurs after 25-35 minutes from start.

Such a system implementation aims to be easy to use and operate avoiding the use of any skilled operator. In addition, the system requires minimal user training. Data are digitally stored

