Dark-adaptometry testing will be carried out by using the novel investigational system described in Section 4.3. Wearable goggles and joystick are given to participants in their switched-on status and held by the subject under test respectively on the forehead, with an elastic strap, and on the dominant hand. For hygienic safety purposes, a non-allergenic disposable tissue will be placed on top of the inner gasket of the goggles that will be in contact with participants' face. Where a disposable tissue would not be available, the inner gasket of the goggles will be accurately cleaned with a sterile isopropanol solution. Participants will sit comfortably throughout the test and wear disposable earphones playing music to drown out external noise and any auditory signals from the embedded electronics when light stimuli are emitted. Testing is non-invasive and is semi-automatic in that the subject under test is required to collaborate actively during the procedure in order to start it and go through it. A responsible collaboration throughout the test will be repeatedly encouraged as testing results are strictly based on the subject's response. The examiner will start the test by triggering a white flash of light through a standard camera flash (e.g., Canon Speedlite 540EZ – Guide Number 54, 1.2 ms duration). The flash will be channelled to the study eye and aims to photo-bleach, hence reset the photoreceptors of the retina. Immediately after the onset of the photo-bleaching flash, the goggles are pulled down over the eyes by the user that will now be exposed to intermittent white light stimuli. Light stimuli are shone automatically inside the goggles after the photo-bleaching flash and until the end of the test. Dark-adaptometry testing will last for about 25-35

minutes and will involve one eye only. This will be randomly allocated by the examiner or will be the only eye meeting the inclusion criteria. As the brightness of the intermittent light stimuli changes throughout the test as well as the time at which they are presented, participants are asked to press either of the joystick's buttons to indicate when the light is visible. The intermittent light features an initial brightness of approximately 4.86 cd/m^2 and becomes dimmer and dimmer overall. The test lasts until participants will not be able to identify any new light stimuli.

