4.11. Primary outcomes

Primary outcome variables for Group 1&2:

- Rod-cone break
- Absolute threshold

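### Protocol and SAP read the primary outcome absolute threshold differently, and the SAP's labels for η4 and θ1 do not fit Eq. 1 as printed

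*SAP*

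**What the plan says.** Protocol section 4.11 lists "Absolute threshold" as one of two primary outcomes. Section 4.8 defines it: "The absolute threshold will be the last measured threshold and recorded as the dimmest light that the subject can detect" at maximum rod sensitivity. The expected value is about 10⁻⁶ cd/m² "at a time of around 30 minutes from the start of the test". The test has no fixed length. Section 4.3 says that the light stimuli "will stop when the absolute threshold is measured, which in normal healthy adults typically occurs after 25-35 minutes from start", and section 4.8 adds: "The test lasts until participants will not be able to identify any new light stimuli".

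The SAP carries the same version and date (2.0, 27/01/2017). It does not name absolute threshold as a rod outcome. Its rod parameters of interest are the rod-cone break, the rod slope and rod sensitivity, the last of these "measured as the minimum sensitivity value of the rod-mediated dark adaptation function around the 40 minutes end of the test".

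The SAP fits two models. Eq. 1 uses one exponential for each phase. Eq. 2 is described as "fitting a single exponential to the cone threshold recovery data and 2 linear components (i.e., S2 and S3) to any rod threshold recovery data". One parameter list serves both equations. It calls η4 the final threshold, or absolute sensitivity, of the rods, and θ1 the absolute threshold of the cones.

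**The concern.** A primary outcome needs one derivation. Here the statistic differs (last against minimum), and so does the stated end of the test (about 25-35 minutes against about 40). Neither document says which governs. An analyst could follow either and obtain a different number for the same participant. That number goes into the SAP's comparison with published dark-adaptation data, which addresses the protocol's first research question, and possibly into the repeatability statistics.

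The parameter labels raise a second, separate problem. Anyone who reads the cone or rod level straight from the Eq. 1 estimates under the printed labels would report the wrong quantity.

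**Working it through.** The plan gives no figure to reproduce on this point. The check sets the definitions side by side and then takes the limits of the printed equations.

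**1. The two read-outs**

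| | Protocol 4.3 and 4.8 | SAP, rod parameters |
|---|---|---|
| Statistic | last threshold measured, described as the dimmest detectable light | minimum of the rod function |
| Scale | luminance threshold | sensitivity |
| Time | when responses end the test, typically 25-35 min | around a 40-min test end |
| Raw or fitted | measured | not stated |
| Model, if fitted | not applicable | not stated |

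Treating rod sensitivity as the counterpart of absolute threshold is an inference. It is supported by section 4.8, which ties absolute threshold to maximum rod sensitivity, and by the SAP's label for η4. If the inference is wrong, the SAP contains no derivation of this primary outcome.

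**2. Direction of the scale.** Protocol section 2 states that threshold and sensitivity are inversely related. Minimum sensitivity is therefore, literally, maximum threshold, the opposite of the dimmest light. The SAP expresses its functions as log threshold against time, so the lowest log threshold is probably meant.

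**3. Last against minimum on one raw record.** The minimum of a set of thresholds that includes the last one cannot exceed the last one. The two are equal when the last is also the lowest. How far they differ otherwise depends on measurement noise and on the number of points near the end, and the documents give neither.

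**4. Limits of Eq. 1 as printed.**

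D = θ1 + θ2·exp(-t/θ3) + η4·exp(-(t - θ5)·h/η6)

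- For t ≤ θ5, h = 0 and the rod term is η4·exp(0) = η4. Once the cone exponential has died away, D is at θ1 + η4. This is the cone plateau.
- As t grows, h = 1 and both exponentials go to 0, so D tends to θ1. This is the final rod level.
- The drop from cone plateau to final rod level is (θ1 + η4) - θ1 = η4.

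The large-t limit is also θ1 with the SAP's logistic switch, and with h moved outside the exponent.

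**5. Limits of Eq. 2.** Before θ5 both rod terms are 0, so the cone plateau is θ1 and the printed label fits. After θ7 the rod part is a straight line with slope θ4 + θ6, so Eq. 2 has no rod plateau. If the SAP's minimum is a fitted value, the model has to be named.

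**6. Size of the label error.** Inputs from protocol section 4.8: rod-cone break about 10⁻³ cd/m² at about 7 min (taken as the cone plateau, -3 log), absolute threshold about 10⁻⁶ cd/m² (taken as the final rod level, -6 log), and starting stimulus 4.86 cd/m² (log10 = 0.69).

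- θ1 = -6, and θ1 + η4 = -3, so η4 = -3 - (-6) = +3.
- For the curves below, θ2 = 0.69 + 3 = 3.69 and θ5 = 7. The values θ3 = 1.5 and η6 = 6 min are assumed. They change the shape but not the limits.

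| Values in Eq. 1 | t = 0 | 6.9 min | 40 min | limit |
|---|---|---|---|---|
| θ1 = -6, η4 = +3 (from the algebra) | 0.69 | -2.96 | -5.99 | -6 |
| θ1 = -3, η4 = -6 (labels as printed) | -5.31 | -8.96 | -3.02 | -3 |

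The first row reproduces the curve the protocol expects. The second falls to about -9 and then rises to -3, which is not dark adaptation.

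**The case against.** The strongest reply on the read-outs is that they are close in intent. The protocol describes its last threshold as the dimmest light detected, stimuli stop only once the absolute threshold has been measured, and the stated times are all approximate. The visit slot in section 4.7 is 45 minutes, which could hold a 40-minute test. This stands in part: on a flat, quiet plateau the two values nearly agree. It does not say which governs when they differ.

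On the labels, the reply is that rod sensitivity is defined as a minimum and cone sensitivity as the plateau of a single exponential fit, so no stated outcome is taken from η4 or from θ1 in Eq. 1. This also stands. A reader might infer that the primary outcome is miscalculated; the documents do not show that. The harm arises only if those estimates are reported under their printed names.

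Four further inferences are tempting and not supported:

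- *That the gap between 25-35 and 40 minutes is a bias of a known number of log units.* Any such figure compares two points on an assumed recovery curve. A test that stops at 25 minutes has no 40-minute value under either document.
- *That the choice of model moves the outcome by a known amount.* The SAP value may be a raw threshold, in which case neither model supplies it. Any size would also depend on which model is assumed true.
- *That the protocol contradicts itself on timing.* Section 2 says "After approximately 30-40 minutes in total darkness, the final rod threshold is achieved", but this is background physiology, discussed around another instrument's curve. It does not specify this device's test.
- *That the remedy is to read Eq. 1 at a fixed time such as 30 minutes.* That value lies above the fitted plateau, gives no observed value for tests that end earlier, and displaces the protocol's own definition.

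**Conclusion.** The concern holds in two limited parts.

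First, a primary outcome has two read-outs that are not reconciled, and the SAP's wording also inverts the scale and leaves open raw or fitted and which model. This rests on the text and on the inference that rod sensitivity is the counterpart of absolute threshold. The documents do not allow the difference to be sized, and it may often be small. The comparison with published data is descriptive, with no stated test or decision limit, so no formal conclusion is shown to change.

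Second, two labels are wrong for Eq. 1 as printed. This is algebra and needs no assumption. On the protocol's typical values, η4 would be about +3 where the final rod level is about -6 log cd/m², and θ1 about -6 where the cone plateau is about -3. Those sizes assume that the typical rod-cone break and absolute threshold stand for the two plateaus.

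Both parts should be corrected, because the repair is cheap and a primary outcome is involved.

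**What to change.** - State one governing read-out for absolute threshold in both documents: by default the protocol's last measured threshold at test end, in log cd/m². Say in the SAP that this is the primary outcome now called rod sensitivity.
- Report the lowest log threshold near test end as a sensitivity analysis. Give the time window, say whether it is raw or fitted and, if fitted, name the model.
- Replace minimum sensitivity with lowest log threshold.
- Reconcile the 25-35 minute and 40-minute statements of test end, leaving the stopping procedure as it is.
- For Eq. 1, relabel η4 as the size of the rod drop and θ1 as the final rod level, and give the cone plateau as θ1 + η4. Keep θ1 as the absolute cone threshold for Eq. 2 only. Alternatively, correct the equation so that the present labels fit.

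The cost is wording in two documents and slightly more analysis of threshold data already stored as .csv files. The device, the test and the visits do not change.

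### Read as SD over mean, the planned wCV is not valid for log-scale thresholds; the SAP should restrict it or define its formula and scale

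*SAP*

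**What the plan says.** The SAP states that the cone and rod functions "were expressed as log threshold luminance vs. time (minutes"). The fitted cone plateau, and the rod sensitivity read from the end of the rod function, are therefore in log units.

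On repeatability the SAP says: "Repeatability coefficient (RC) and within-case coefficient of variance (wCV) were calculated starting from the within-subject variance", for each participant with at least two visits. The next sentence adds an ICC for each age group. The SAP does not give a formula for the "within-case coefficient of variance (wCV"), name the parameters it applies to, or say whether thresholds are first converted back to luminance.

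Protocol section 4.11 lists two primary outcomes, rod-cone break and "Absolute threshold". Section 4.8 describes the typical healthy absolute threshold as a "logarithmic light intensity around 10^{-6} cd/m^2 at a time of around 30 minutes". It also gives a typical luminance at the rod-cone break, "logarithmic light intensity around 10^{-3} cd/m^2 at a time of around 7 minutes", but the SAP defines the rod-cone break itself as a time in minutes.

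**The concern.** A coefficient of variation divides an SD by a mean, so it needs a scale with a true zero. Log luminance has none. Changing the unit multiplies every luminance by a constant, which adds a constant to every log value: the mean moves and the SD does not. The ratio therefore depends on the unit as well as on the device.

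Whether results are repeatable is one of the protocol's research questions (section 3, question III), and one of the two primary outcomes is on this scale. A wCV of a few per cent for the absolute threshold would be read as high precision, although the luminance at threshold might vary between visits by a large fraction of its own value. The figure could also not be set against a wCV from an instrument reporting in another unit.

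**Working it through.** The plan states no wCV and no within-subject SD, so there is no figure to reproduce. The check takes the ordinary definition and the protocol's typical threshold.

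**Inputs**
- Log mean of the absolute threshold: log10(10^-6) = -6 in cd/m² (Protocol 4.8).
- Starting luminance: 4.86 cd/m², log10 = +0.69 (Protocol 4.8), so the log scale crosses zero within one test.
- Within-subject SD, sw: assumed at 0.1, 0.15, 0.3 and 0.5 log10 unit.

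**Formulas**
- wCV = sw / |mean of log threshold|
- RC = 1.96 × √2 × sw, in log units; as a luminance ratio, 10^RC
- CV on the luminance scale = sqrt(exp((2.303 × sw)²) − 1), taking within-subject error as normal on the log scale

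**Absolute threshold.** The log mean is -6 in cd/m² and -6 + 3 = -3 in mcd/m².

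| sw (assumed) | wCV, cd/m² | wCV, mcd/m² | RC, log units | 10^RC | Luminance-scale CV |
|---|---|---|---|---|---|
| 0.1 | 0.1/6 = 1.7% | 0.1/3 = 3.3% | 0.28 | 1.9 | 23% |
| 0.15 | 0.15/6 = 2.5% | 0.15/3 = 5.0% | 0.42 | 2.6 | 36% |
| 0.3 | 0.3/6 = 5.0% | 0.3/3 = 10.0% | 0.83 | 6.8 | 78% |
| 0.5 | 0.5/6 = 8.3% | 0.5/3 = 16.7% | 1.39 | 24 | 166% |

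The two wCV columns describe identical data. RC, 10^RC and the luminance-scale CV are the same in either unit. In microcd/m² the log mean would be 0 and wCV undefined.

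**Direction of the error.** At sw = 0.3, a one-SD error is a two-fold change in luminance (10^0.3 = 2.0), yet wCV at -6 is 5%. At the starting luminance the same SD gives 0.3/0.69, about 44%, still below 78%. wCV exceeds the luminance-scale CV only when the log mean lies within 0.3/0.78 = 0.38 of zero; at a log mean of 0.1, for example, it would be 300%. So wCV understates the error far from log 0 and overstates it close to log 0.

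**Parameters not affected.** For a rod-cone break at 7 minutes (Protocol 4.8) with an assumed SD of 1 minute, wCV is 1/7 = 14.3% in minutes and 60/420 = 14.3% in seconds. The cone and rod time constants and the time of the S2-to-S3 transition behave in the same way. The S2 and S3 slopes do not change when a constant is added to the log scale.

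**The case against.** The strongest reply is that the SAP never says wCV is sw divided by the mean log threshold. The log-normal formula above also starts from the within-subject variance, fits the SAP's wording and does not depend on the unit. This stands: the SD-over-mean reading is the natural one, but it is an inference. It does not remove the point, because the SAP neither states the alternative nor excludes the log thresholds.

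Second, RC and ICC are planned alongside wCV. Neither changes when a constant is added to the log values. This stands, and it limits the harm.

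Third, the device's luminances are given in cd/m² throughout, so a change of unit may seem hypothetical. The other luminance unit in the protocol, mL for the reprinted benchmark curve (Figure 1), would move wCV only from 5.0% to 4.6% at sw = 0.3 (1 mL = 3.18 cd/m², so the log mean is -6.50). Comparison between the age groups would also be little distorted: with assumed group means of -6.0 and -5.5 and sw = 0.15 in both, wCV is 2.5% and 2.7%. Both figures are fair. They do not cure the understatement, which arises in cd/m² itself.

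Fourth, wCV is not a named primary or secondary outcome, and no acceptance limit is tied to it. That also stands.

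**Conclusion.** On the ordinary SD-over-mean reading, wCV is not a valid repeatability measure for the absolute (rod) threshold or the cone threshold. At the protocol's typical absolute threshold in cd/m², assumed SDs from 0.1 to 0.5 log unit would be reported as 1.7% to 8.3%, where the luminance-scale CV runs from about 23% to 166%. These sizes rest on the assumed SDs, on a log mean of -6 and on log-normal within-subject error.

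A reader might infer that wCV would look excellent whatever the device does. The documents do not support that: in a fixed unit wCV rises in proportion to the SD (an SD of 1.0 gives 1.0/6 = 16.7%), and close to log 0 it exaggerates the error. Nor is the luminance of about -3 log cd/m² at the rod-cone break a second affected primary outcome, since the SAP analyses that break as a time. Nor does the plan leave threshold repeatability unmeasured, since RC and ICC cover it. The defect concerns one statistic on the log-threshold parameters and is worth correcting because the correction is nearly free.

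**What to change.** In the SAP's repeatability paragraph, limit wCV to parameters whose value does not depend on the luminance unit, such as rod-cone break time and the time constants. For the absolute and cone thresholds, report the within-subject SD and RC in log units, with the back-transformed ratio 10^RC. If a CV is wanted for thresholds, state that it is sqrt(exp((2.303 × sw)²) − 1), with sw in log10 units.

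The cost is one SAP sentence and a less flattering percentage for thresholds. No further data or visits are needed, because every quantity comes from the within-subject variance already planned.
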